8.2. Statistical and Analytical Plans

Our primary outcome will be attainment of beta-lactam therapeutic targets: 100%fT>MIC, 40-70%fT>5xMIC, 100%fT>5xMIC. Proportion of patients, who achieve beta-lactam therapeutic targets, during the first and subsequent TDM will be determined. For the group of patients, who require dose adjustments, after the 1st TDM and need further TDM, the proportion of patients who require dose increment and dose reduction, the number of TDM performed to achieve therapeutic target and the mean/median time required to achieve therapeutic target will also be evaluated.

Correlation of primary outcomes will be made to the following secondary outcomes.

- a. Mortality at the end of therapy and within 30-day mortality.
- b. Days to defervescence
- c. Days to resolution of white blood cell count, pro-calcitonin and C-reactive protein.

Any incidence of adverse effects related to beta-lactam therapy will also be reported and evaluated in correlation to beta-lactam levels.

For univariate analyses with binomial outcomes (e.g. mortality), Chi-square test or Fisher's exact test will be performed where appropriate. For univariate analyses with time-dependent outcomes (e.g. days to defervescence, days to resolution of inflammatory markers), Kaplan-Meier analysis will be performed. For univariate analyses with continuous outcome variables (e.g. APACHE II score, SOFA score), Student's t-test and Mann-Whitney-U test will be performed for parametric and non-parametric data respectively. Multivariate analyses will then be performed to include potential confounders such as APACHE II score, SOFA score, Charlson comorbidity index, use of beta-lactam as culture-directed therapy, presence of multi-drug resistant infection, and presence of concurrent infections requiring additional antibiotics. Logistic regression will be used for binomial outcomes (mortality) while Cox regression will be used for time-dependent outcomes (days to defervescence, days to resolution of inflammatory markers).

To evaluate population pharmacokinetics in various patient groups, a specialised pharmacokinetic software will be used to develop population pharmacokinetic models. Model simulation will then be performed to design empiric dosing recommendations to guide local practice.

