In addition, therapeutic targets for beta-lactam TDM are not well established, with varying practices world-wide [33]. None the beta-lactam targets have been extensively clinically validated. Beta-lactams exhibit time-dependent bactericidal activity and their pharmacokinetic/pharmacodynamics therapeutic target is characterised by the percentage of the dosing interval for which the unbound beta-lactam concentration is maintained above the MIC (fT>MIC). Based on in vitro and in vivo studies, the targets are 40% of the dosing interval (40% fT>MIC) for carbapenems, 50% (50% fT>MIC) for penicillins and 60-70% (60-70%) fT>MIC) for cephalosporins [34-36]. However, clinical observational studies suggest a longer fT>MIC for optimal clinical outcomes (mortality, clinical response, duration of hospital stay) [4,37-39]. In addition, some studies have shown that higher plasma concentrations (fT>4- $5 \times MIC$) may be required for maximal bactericidal activity [40-41], optimal tissue penetration [42-44], optimal clinical response and microbial eradication in patients with pneumonia [45] and

prevention of resistance [6,46]. Centres, that perform beta-lactam TDM, have used the targets 100%fT>MIC, 40-70%fT>4-5xMIC (depending on type of beta-lactam) or 100%fT>4-5xMIC [33] but no studies have compared these targets in terms of clinical outcomes achieved. In this study, we plan to evaluate the correlation between beta-lactam target and clinical outcomes and to determine which beta-lactam target is optimal for clinical practice.

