For all patients, 4 sets of blood samples (5 mL each) will be obtained via venipuncture or existing cannula access within a dosing interval. We propose to obtain 4 samples for each TDM in this study to generate more robust and accurate drug concentration-time curves for calculation of target attainment and to better characterise patients' pharmacokinetic profiles. For most patients (except those on intermittent extracorporeal therapies), blood samples will be obtained during end of infusion, 1 hour after infusion, 2 hours after infusion and within 30 minutes of the next scheduled dose (i.e. trough level) if beta-lactam is given as short infusion over \leq 30 minutes. If beta-lactam is given as extended infusion (e.g. 3-4 hours), blood samples will be obtained at mid-infusion, end of infusion, 1 hour after infusion and within 30 minutes of the next scheduled dose (i.e. trough level). For patients on intermittent extracorporeal therapies (e.g. intermittent dialysis), blood samples will be obtained at end of beta-lactam infusion, at the beginning of dialysis, end of dialysis and within 30 minutes of the next scheduled dose (i.e. trough level).

To ensure therapeutic targets are reached, further blood sampling, according to the schedule above, may be performed after dose adjustments or when there is a change in patient's clinical status (e.g. change in dialysis settings, change in renal function), which may warrant change in beta-lactam dosing regimen. Blood sampling for TDM will be stopped when beta-lactam has been discontinued, when therapeutic targets are achieved or when patient has been discharged from the hospital.

Assay of beta-lactam levels

All blood samples will be sent to our research laboratory for assay via liquid chromatographytandem mass spectrometry. All blood samples will be labelled by our study team using subject codes (no patient identifiers will be used).

Beta-lactam TDM and Dose Individualisation

The treating physicians will have the option to know the results of the TDM, once available. An infectious disease-trained pharmacist may make recommendations on dose adjustments based on the TDM results. However, accepting these recommendations will be at the discretion of the treating physicians.

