The infectious disease trained pharmacist may use pharmacokinetic software to analyse drug concentration-time profile to guide dose adjustments. If available, dose recommendations will be based on the MIC of the known pathogen, which will be provided by the local microbiology laboratory. Where no pathogen was formally identified, MICs are not available or cultures are pending, the highest MIC (according to the Clinical and Laboratory Standards Institute (CLSI criteria) for susceptible bacteria to the antibiotic will be assumed.

Data Collection

All patients will be followed up from study entry to 30 days from study entry, hospital discharge or mortality, whichever occurs earlier.

Data will be collected from electronic medical records, using a standardised data collection form. These will include:

•patient demographics (unique identifier, age, gender, race, body weight, height, comorbidities including Charlson Comorbidity Index)

•pharmacokinetic-specific data (use of extracorporeal therapy/dialysis and settings, urine output, serum creatinine, albumin)

•clinical data (temperature, blood pressure, heart rate, respiratory rate, mortality, cause of mortality, severity of illness indicators such as APACHE II score and SOFA score, incidence of beta-lactam-related adverse events/side effects as reported by primary physicians, admission and discharge date from hospital and from intensive care unit if applicable)

•laboratory data (albumin, serum creatinine, procalcitonin, CRP, total white count)

•infection-related data (site and type of infection, pathogens isolated and their susceptibility results and reported minimum inhibitory concentrations)

•drug-related data (beta-lactam dosing regimens including any change to dosing regimens, concurrent antibiotic use history and their dosing regimens, presence of any drug which may interact with beta-lactams or interfere with beta-lactam assay results)

•beta-lactam assays levels, attainment of therapeutic targets and whether dose adjustments were made

Data will be stored in a password-protected database and only study team members will have access to data. Identifiers will be stored separately from collected data. Data collection forms will not contain identifiers (e.g. NRIC, name, date of birth). All hardcopy data collection forms and consent forms will be stored under lock and key in the cupboard at [name] of

Pharmacy department in Singapore General Hospital.

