8. SAMPLE SIZE AND STATISTICAL METHODS

8.1. Determination of Sample Size

Patients will be recruited until 320 assays are performed (based on budget of \$40,000, estimated cost of each assay is \$125, number of assays = 40,000/125 = 320 assays). This will be roughly equivalent to 80 patients, assuming patients will have 4 assays each.

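### Section 8.2 relates target attainment to mortality and recovery without naming the TDM that defines exposure; if later attainment is used as a fixed exposure, survival and length of stay are built into it

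*Combined protocol and SAP*

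**What the plan says.** Section 8.2 takes attainment of three targets as the primary outcome and counts it on more than one occasion: "Proportion of patients, who achieve beta-lactam therapeutic targets, during the first and subsequent TDM will be determined". It continues: "Correlation of primary outcomes will be made to the following secondary outcomes", namely mortality, days to defervescence and days to resolution of inflammatory markers. Mortality is compared by chi-square or Fisher's exact test and recovery times by Kaplan-Meier. For the adjusted models, "Logistic regression will be used for binomial outcomes (mortality) while Cox regression will be used for time-dependent outcomes". The covariates are severity scores, comorbidity and infection characteristics. Nothing in 8.2 says whether exposure is attainment at the first, last, any or each TDM, or when follow-up starts. Secondary objective 1 in Section 2 speaks only of achieved targets.

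Section 5 (Blood sampling) plans a first four-sample TDM for every patient. Further sampling "may be performed after dose adjustments or when there is a change in patient's clinical status". It also has stopping rules: "Blood sampling for TDM will be stopped when beta-lactam has been discontinued, when therapeutic targets are achieved or when patient has been discharged".

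**The concern.** A patient who misses the target at the first TDM can become an attainer only by living, staying on the drug and remaining in hospital until a re-check. If later attainment is entered as though known from the start, patients who die before a re-check stay in the not-attained group because they died. Patients who recover and leave stay there because they recovered. The first makes attainment look protective and the second makes it look harmful. Adjusting for APACHE II, SOFA, Charlson and the other listed covariates does not remove either, because the problem is time at risk and not baseline severity.

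What is at stake is secondary objective 1 and the aim in Section 1 "to determine which beta-lactam target is optimal for clinical practice". A difference produced by who was available for re-measurement could be read as an effect of reaching a target. The descriptive attainment proportion at the first TDM is not affected.

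**Working it through.** **The plan's own figure.** Section 8.1: 40,000 / 125 = 320 assays, and 320 / 4 = 80 patients. Both reproduce. Section 5 takes four samples per TDM, so 80 patients corresponds to one TDM each. Because "Patients will be recruited until 320 assays are performed", every re-check lowers the number of patients.

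**Inputs.** The documents give the 320-assay cap and four assays per TDM. First-TDM attainment of 50% is in line with the Section 2 hypothesis that dosing is suboptimal in at least half of patients. The rest are assumptions: no true effect of attainment; 30-day mortality 25%; 60% success at a single re-check; a share *e* of below-target deaths (10–40%) before the re-check; a share *r* of the remaining below-target patients re-checked.

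**One case per 100 patients, e = 20%, r = 50%.**
- At target at the first TDM: 50 patients, 12.5 deaths. Below target: 50 patients, 12.5 deaths. By first-TDM status the difference is 25% − 25% = 0.
- Below-target deaths before the re-check: 0.20 × 12.5 = 2.5. Remaining: 47.5 patients, 10 deaths.
- Re-checked: 0.50 × 47.5 = 23.75 patients, 5 deaths. Newly attained: 0.60 × 23.75 = 14.25 patients, 3 deaths.
- Ever attained: 64.25 patients, 15.5 deaths = 24.12%. Never attained: 35.75 patients, 9.5 deaths = 26.57%.
- False difference, never minus ever: 2.4 points.
- Patients affordable: 320 / (4 × 1.2375) = 64.6.

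**Over the range of e** (Fisher's exact test, two-sided 5%, 20,000 simulated studies per setting, N limited by the assay cap):

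| Re-checked | N | False difference at e = 10 / 20 / 30 / 40% (points) | Fisher rejection, ever vs never (%) |
|---|---|---|---|
| 0% | 80 | 0 | – |
| 25% | 71–72 | 0.6 / 1.1 / 1.7 / 2.3 | 3.7 / 3.8 / 4.1 / 4.3 |
| 50% | 64–65 | 1.2 / 2.4 / 3.7 / 4.9 | 3.8 / 4.3 / 4.8 / 5.7 |

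By first-TDM status, rejection is 3.2–3.7% throughout. At 50% re-checked, varying first-TDM attainment over 30–70% and re-check success over 40–80% widens the range to 0.6–8.5 points. The top comes from 30% attainment with 80% success. The 70% end sits outside the plan's own hypothesis.

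**Direction.** Suppose 40% of the below-target patients alive at the re-check have already left, with 5% mortality. For e = 20%, r = 50%:
- Leavers: 0.40 × 47.5 = 19 patients, 0.95 deaths. Still present: 28.5 patients, 9.05 deaths.
- Re-checked: 14.25 patients, 4.525 deaths. Newly attained: 8.55 patients, 2.715 deaths.
- Ever attained: 15.215 / 58.55 = 25.99%. Never attained: 9.785 / 41.45 = 23.61%.
- False difference: −2.4 points. Over e = 10–40% it runs from −3.7 to +0.2.

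**Against sampling error.** The 95% half-width is 1.96 × √[p₁(1−p₁)/n₁ + p₂(1−p₂)/n₂]. In the e = 20%, r = 50% case without early leavers, n₁ = 41.5 and n₂ = 23.1, which gives about 22 points. At 25% re-checked it is about 20. These rest on 16–18 expected deaths.

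**The case against.** The strongest reply is that the bias depends on an analysis the plan never states. A reader might infer that 8.2 commits to an *ever attained* exposure. It does not; it leaves the choice open. A reader might also infer that the Cox models hold exposure fixed. The text names Cox regression without saying how attainment enters, and Cox can carry a time-varying covariate. Only the chi-square, Fisher and logistic analyses of mortality are fixed-exposure by nature. Both points stand. What remains is that an analyst could use later attainment as a fixed exposure without departing from the plan.

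Second, the sizing assumes one TDM per patient, where the bias is zero, and re-checks are optional after discretionary dose changes. This also stands. It rules out leaning on the extreme in which every remaining below-target patient is re-checked. The same arithmetic then gives 3.4–12.7 points, with rejection up to 13.3% and N of 54–55, but the sampling rules do not make that case plausible.

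Third, the bias at 25–50% re-checked is small beside a half-width of 20–22 points. That is true: 4.9 / 22 is under a quarter. The harm is a distorted estimate of unknown sign, not a high false-positive rate.

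Fourth, the subsequent-TDM proportion might be read as one half of a before/after comparison with the first. The plan proposes no such comparison, so that criticism is not made here. The proportion only needs its denominator shown.

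Finally, first-TDM exposure labels patients corrected soon afterwards as non-attainers and may dilute a real association with achieved targets. That is a genuine cost of the fix.

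**Conclusion.** The point holds as a cheap improvement to a secondary objective. Section 8.2 leaves the exposure occasion and the time origin undefined, and the Section 5 sampling rules make later attainment depend on being alive, on treatment and in hospital. Under the stated assumptions, a fixed ever-attained exposure gives a false mortality difference of about 0.6–2.3 points at 25% re-checked and 1.2–4.9 at 50%, with rejection of 3.7–5.7%. The sign can reverse when early recoverers leave. The difference is zero by first-TDM status or with no re-checks.

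These sizes are illustrative: mortality, re-check success, timing of deaths and re-check frequency are not in the documents. The model re-checks only below-target patients, whereas Section 5 also allows re-sampling after clinical change and 8.2 foresees dose reductions. One attainment figure stands in for three targets of different stringency. All figures concern mortality; the same mechanism applies to defervescence and marker resolution, but its size there is not quantified.

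**What to change.** Amend 8.2 only; the sampling rules in Section 5 can stay as they are.

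1. In the main correlations with mortality, defervescence and inflammatory markers, define exposure as attainment of each target at the first TDM, with follow-up counted from that TDM.
2. Relate later attainment to outcome only as a sensitivity analysis, using a time-varying covariate in a Cox model (for mortality as well) or a landmark analysis.
3. Report subsequent-TDM attainment as n/N of those re-sampled, with the numbers who died, stopped the drug or were discharged before a re-check.

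The cost is about three sentences and no extra assays. TDM dates are already needed for the planned time-to-target summary. Date of death should be recorded explicitly: the data list in Section 5 has "mortality, cause of mortality, severity of illness indicators" and discharge dates, but does not name it.

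There are three downsides. The main analysis gives no credit for targets reached after dose adjustment. The sensitivity analysis will be imprecise, with about 16–18 deaths at 25–50% re-checked under the assumed mortality. Patients already afebrile at the first TDM leave the defervescence analysis.

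### The plan does not say how patients who never reach target enter the mean/median time to target; a plain summary would understate the time

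*Combined protocol and SAP*

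**What the plan says.** Section 8.2 of the combined protocol and SAP makes target attainment the primary outcome, reported as proportions at the first and later TDM rounds. It then adds descriptive summaries. "For the group of patients, who require dose adjustments, after the 1st TDM and need further TDM", it will report how many need a higher or a lower dose and how many TDM rounds were needed to reach target, and "the mean/median time required to achieve therapeutic target will also be evaluated". It gives no time origin and no rule for patients who do not reach target. It also does not say which of the three listed targets defines the event.

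Section 5 (Blood sampling) sets the stopping rule: "Blood sampling for TDM will be stopped when beta-lactam has been discontinued, when therapeutic targets are achieved or when patient has been discharged". Repeat sampling is optional; it "may be performed after dose adjustments or when there is a change" in the patient's clinical status. Section 5 (Data Collection) adds: "All patients will be followed up from study entry to 30 days from study entry, hospital discharge or mortality, whichever occurs earlier".

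On methods, section 8.2 says: "For univariate analyses with time-dependent outcomes (e.g. days to defervescence, days to resolution of inflammatory markers), Kaplan-Meier analysis will be performed". For the adjusted analysis, "Cox regression will be used for time-dependent outcomes (days to defervescence, days to resolution of inflammatory markers". Time to target appears in neither list.

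**The concern.** Time to target and number of TDM rounds to target are time-to-event quantities. Of the three stated reasons for ending TDM sampling, only one is the event itself. A patient who stops the drug, goes home or dies while still off target has no value for either summary. A patient who is never resampled has none either, even if the target was in fact met.

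A mean cannot be calculated over missing values without a rule, and the same holds for a median unless the patients who never reach target are given a rank. With no rule, the natural execution is to average over patients seen to reach target. Early attainers are more likely to be seen, because they reach target before anything else ends observation. Such a summary would make TDM-guided adjustment look quicker, and in need of fewer rounds, than it was for the group treated. The section 1 rationale presents the study as an evaluation of the feasibility of beta-lactam TDM, so readers will take note of this number.

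**Working it through.** **The plan's own figures.** Section 8.1: 40,000 / 125 = 320 assays, and 320 / 4 = 80 patients. Both reproduce. The documents state no figure for time to target, for the share reaching it, or for the share lost beforehand.

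**Size of the group.** Section 5 takes 4 samples per TDM, so 320 assays pay for exactly one TDM in each of 80 patients. If a fraction f has one repeat TDM, the budget covers N = 320 / (4 × (1 + f)) patients, of whom N × f are repeated:

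- f = 0.25: 64 patients, 16 repeated
- f = 0.50: about 53 patients, about 27 repeated
- f = 0.75: about 46 patients, about 34 repeated

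The values of f are assumptions. Section 2 hypothesises suboptimal dosing in at least half of patients. In a group this small, a few omitted patients can move the median.

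**Direction and illustrative size of the understatement.** All inputs here are assumed:

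- Time to target is exponential, with a median of m = 4 days if nobody left, so λ = ln 2 / 4 and the mean is 4 / ln 2 = 5.8 days.
- Leaving (drug stop, discharge or death) is independent and exponential with rate c.
- The share reaching target is P = λ / (λ + c).

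The formulas are:

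- Median among those who reach target: ln 2 / (λ + c) = P × m
- Mean among those who reach target: 1 / (λ + c) = P × 5.8
- Kaplan-Meier median with leavers censored: m
- Cumulative-incidence median with leavers as competing events: −ln(1 − 0.5/P) / (λ + c), which exists only if P exceeds 0.5

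| P | Attainers-only median (days) | Attainers-only mean (days) | Kaplan-Meier median (days) | Cumulative-incidence median (days) |
|---|---|---|---|---|
| 0.9 | 3.6 | 5.2 | 4.0 | 4.2 |
| 0.8 | 3.2 | 4.6 | 4.0 | 4.5 |
| 0.7 | 2.8 | 4.0 | 4.0 | 5.1 |
| 0.6 | 2.4 | 3.5 | 4.0 | 6.2 |
| 0.5 | 2.0 | 2.9 | 4.0 | not reached |

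Simulating 400,000 pairs per row agrees with the attainers-only and Kaplan-Meier columns to within about 0.02 day.

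Relative to the median if nobody left, the attainers-only median is too short by 1 − P: 10% at P = 0.9 and 30% at P = 0.7. The last two columns answer different questions. Kaplan-Meier with censoring estimates the time if nobody left. Cumulative incidence estimates what happens to the patients actually treated. The attainers-only figure is shorter than both.

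**Follow-up wording.** The design paragraphs of section 5 follow patients to the latest of end of therapy, 30 days from the start of the beta-lactam, discharge or death. Data Collection in the same section uses the earliest of 30 days from study entry, discharge or death. No end date for this analysis can be set until the two are reconciled.

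**The case against.** A reader might infer that the plan restricts the calculation to patients who reach target, and that the study will therefore report a time biased short. The text does not say so. Its stated group is everyone who needs adjustment and further TDM. The Kaplan-Meier sentence introduces its outcomes as examples, which leaves room for time to target, and a median could come from that curve. This stands: the defect is a missing rule, not a stated wrong one. It does not remove the problem. The Cox list is not framed as examples and omits time to target, and a plain mean is named that no Kaplan-Meier curve supplies. Kaplan-Meier would also need a rule for death, discharge and drug discontinuation, since none of these is simple censoring when the question is attainment on therapy.

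A reader might also infer that these are the study's main feasibility results. The documents do not support that. The primary objective in section 2 is the proportion of suboptimal levels and the need for dose adjustment, and neither secondary objective mentions time to target. There is no comparator, and no test or decision uses this number. The proportion at target, reported beside it, would make non-attainment visible, although it would not correct the time.

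Finally, the size is assumed. The 4-day median, the leaving rates and continuous observation of attainment are not in the documents. To say that the reported median would be half the truth when 50% reach target takes the time if nobody left as the truth. The cumulative incidence recommended here does not estimate that quantity, and in that case its median is not reached at all.

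**Conclusion.** The point holds as a gap with a predictable direction. Section 8.2 plans a mean/median time to target and a count of TDM rounds to target, section 5 ensures that observation can end before target, and nothing says how those patients are counted. If they are left out, the time is understated. The size cannot be determined from the documents. The 10% and 30% figures rest on exponential times, independent leaving and assumed attainment shares of 90% and 70%. The consequence is limited to a descriptive secondary summary and does not touch the primary proportions. The change is worth making because a better method is available at little cost.

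**What to change.** In section 8.2, replace the mean/median time to target as follows:

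- **Denominator:** all patients who need a dose adjustment after the first TDM, whether an increase or a reduction, and whether or not they are resampled.
- **Event and origin:** attainment of each listed target separately, counted from the date of the first TDM. All three targets are minimum exposures, so also state what counts as attainment for a patient whose dose is to be reduced.
- **Estimate:** cumulative incidence of attainment, with death, drug discontinuation and discharge before target as competing events.
- **Report:** the proportion at target by fixed days and after each successive TDM on that same denominator, the median if reached, and the number never observed to reach target. Drop the plain mean.

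In section 5, list TDM sampling dates explicitly among the data collected; assay levels are listed there, but sampling dates are not. Reconcile the two statements on the end of follow-up.

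The cost is SAP wording, one more field on the data form, a little more analysis, and probably a less favourable time to target than a plain average would show.

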4.3. Inclusion Criteria

- a) Age ≥ 21 years old
- b) Admitted to Singapore General Hospital
- c) Receiving beta-lactams for documented or suspected infection
- d) With indication for beta-lactam TDM: critically ill, altered pharmacokinetics (burns, obese, on extracorporeal therapy e.g. dialysis), immunocompromised (haematology/oncology patients), resistant pathogens, deep-seated infections, suspected

or at risk for adverse effects

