5. STUDY DESIGN AND PROCEDURES/METHODOLOGY

This is a prospective observational study conducted in Singapore General Hospital from October 2019 to September 2020. Patients will be screened for eligibility using criteria 4.3 and 4.4. If women of childbearing age are eligible, the beta HCG result taken during the potential subject's course of hospitalisation will be used to exclude pregnant women. If no beta HCG result is available, clinical case notes will be referred to confirm non-pregnancy status.

Eligible patients will be approached by their treating physicians to seek their consent to be referred to the study team. Informed consent will be taken directly from the patient by the study team once patient is agreeable to be referred to the study team. For subjects who do not have the mental capacity to exercise rational judgement, primary physician will assess and document their mental capacity using the Documentation of Capacity form and substituted consent will be obtained by the study team from the spouse, parent, guardian, or legally acceptable representative of the subject. Consent for continued participation will be obtained from patient directly when he regains mental capacity to give informed consent.

Blood sampling and data collection will only commence once informed consent has been taken. Subjects may withdraw voluntarily from participation in the study at any time. Once they have withdrawn from the study, all subsequent blood sampling and data collection will be discontinued.

All patients will be followed up until end of beta-lactam therapy, 30 days from commencement of beta-lactam therapy, hospital discharge or mortality, whichever occurs later.

Blood sampling:

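### Section 5 gives two contradictory follow-up rules, and under one of them the 30-day and end-of-therapy mortality in Section 8.2 cannot be measured; 8.2 also leaves the exposure TDM and death before recovery undefined

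*Combined protocol and SAP*

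**What the plan says.** Section 5, before the blood-sampling text, follows all patients to the end of beta-lactam therapy or "30 days from commencement of beta-lactam therapy, hospital discharge or mortality, whichever occurs later". The Data Collection part of the same section says: "All patients will be followed up from study entry to 30 days from study entry, hospital discharge or mortality, whichever occurs earlier". Both are current text.

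Section 8.2 lists "Mortality at the end of therapy and within 30-day mortality" as the first secondary outcome and gives no day 0. Section 4.2 identifies patients once beta-lactam therapy has been initiated, and Section 5 adds that "Blood sampling and data collection will only commence once informed consent has been taken".

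On exposure, Section 8.2 says "Proportion of patients, who achieve beta-lactam therapeutic targets, during the first and subsequent TDM will be determined", and then "Correlation of primary outcomes will be made to the following secondary outcomes". It does not say which TDM occasion makes a patient an attainer in those correlations. Section 5 stops TDM sampling on drug discontinuation, target attainment or discharge.

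For days to defervescence and to resolution of white cell count, procalcitonin and C-reactive protein, Section 8.2 names Kaplan-Meier and Cox regression. It gives no time origin and no rule for death or discharge before recovery.

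**The concern.** Relating target attainment to mortality and clinical response is secondary objective 1 (Section 2), and Section 1 says the study is to determine which target is best for practice. The outcomes must therefore be collected and defined in one way.

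As written, two analysts could count different deaths, use different day-30 windows and classify different patients as attainers. The follow-up conflict is the serious part, because a death that was never collected cannot be recovered by later analysis. The exposure and recovery gaps can still be closed by wording in the analysis plan.

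**Working it through.** **Follow-up rules side by side**

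| | Section 5, opening text | Section 5, Data Collection |
|---|---|---|
| Rule | latest event | earliest event |
| Day-30 origin | start of beta-lactam | study entry |
| End of therapy in the list | yes | no |
| Death after discharge, before day 30 | collected | not collected |

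Section 8.2 states no origin, so it does not settle the conflict. Under the second rule, end-of-therapy mortality is also lost when therapy continues past discharge or past 30 days from entry. Section 4.3 admits "immunocompromised (haematology/oncology patients), resistant pathogens, deep-seated infections"; therapy length is not stated. Read literally, the first rule has its own flaw: a latest-of list that includes death has no end for survivors.

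**The plan's own figure.** 40,000/125 = 320 assays and 320/4 = 80 patients, as in Section 8.1. The documents give no mortality, discharge or recovery rates, so every rate below is an assumption.

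**Deaths missed under the earliest-event rule.** Let h be the in-hospital death hazard, d = 1/(mean days to discharge), and kh the death hazard after discharge.

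- Recorded: R = h/(h+d) × (1 − exp(−30(h+d))).
- Unrecorded: U = the integral over u from 0 to 30 of d·exp(−(h+d)u) × (1 − exp(−kh(30−u))).
- h is solved so that R + U = 0.20, that is 0.20 × 80 = 16 deaths.

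| Mean days to discharge | k | h per day | Deaths recorded | Deaths missed |
|---|---|---|---|---|
| 30 | 0.1 | 0.0114 | 15.1 | 0.9 |
| 15 | 0.25 | 0.0132 | 12.0 | 4.0 |
| 10 | 0.5 | 0.0114 | 7.9 | 8.1 |

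Recorded mortality runs from 18.9% (top row) down to 9.8% (bottom row). The bottom row implies that 87% are discharged alive by day 30 and that 12% of those die by day 30. A cruder route: if 40–80% of 80 patients leave before day 30, status is unknown for 32–64. At 2–10% post-discharge mortality, the missed deaths run from 80 × 0.4 × 0.02 = 0.6 to 80 × 0.8 × 0.10 = 6.4.

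**Day-30 origin.** With a constant hazard, −ln(0.8)/30 = 0.00744 per day, mortality to day 30 from entry is 20.0%. If entry is g days after therapy start, mortality among those enrolled to day 30 of therapy is 1 − exp(−0.00744 × (30 − g)): 18.8% for g = 2 and 17.0% for g = 5.

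**Exposure TDM.** A later TDM requires the patient to be alive and still on therapy. Simulate no true effect, with 50% attaining at the first TDM, 60% of the rest attaining at a repeat on days 2–7 if alive, and death hazard 0.01 per day. Mortality is then 24.7% in those who ever attained and 30.5% in the others: OR = (0.247/0.753)/(0.305/0.695) = 0.75. Here every surviving non-attainer is resampled. In a separate simulation with 20% mortality, repeats at 2–5-day gaps, 70% success and therapy length unrelated to prognosis, only a quarter of patients were eligible for one retest; the OR was 0.92–0.96. For scale, 40 per group at 20% mortality (8 deaths, 32 survivors) gives SE(log OR) = √(2 × (1/8 + 1/32)) = 0.559, a null 95% interval of 0.33–2.99.

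**Death before recovery.** Take a recovery hazard of 0.06 per day and a death hazard of 0.00744 (20% net mortality).

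- 1 − KM with deaths censored: 1 − exp(−1.8) = 83.5%.
- Cumulative incidence: 0.06/0.06744 × (1 − exp(−30 × 0.06744)) = 77.2%.

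The excess is 6.3 points. At recovery hazards of 0.03 and 0.10 the pairs are 59.3% v 54.1% and 95.0% v 89.4%.

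**The case against.** - **Post-discharge deaths may be visible anyway.** Section 5 says "Data will be collected from electronic medical records, using a standardised data collection form", and those records may show some later deaths. But no part of the plan says they will be searched after discharge, and the Data Collection rule says follow-up has ended. The contradiction stands.
- **The missed-death range rests on assumptions.** This is correct, and the upper end is stretched. The range illustrates size; the conflict itself needs no assumed rate.
- **Nobody has planned to use ever having attained as a fixed exposure.** True: the plan neither chooses nor excludes it. Section 8.1 budgets four assays per patient, about one TDM each, so repeats may be few and the distortion small beside sampling error. What stands is that the classifying TDM must be named.
- **A reader might infer that the bias could run either way, or that any analysis of later attainment is unsafe.** The documents do not support this. Section 8.2 already plans adjustment for APACHE II, SOFA and Charlson index, which should remove much of any distortion from sicker patients being resampled or treated longer, as far as those scores capture prognosis. Adjustment does not cure the fixed ever-attained classification, because at equal prognosis a patient who dies before a retest still counts as a non-attainer.
- **First-TDM exposure is not shown to be unbiased.** Correct. It shows no effect in such simulations only because attainment was drawn independently of outcome. It is a simple choice, and confounding remains.
- **Section 8.2 does not say deaths are censored, and Cox remains valid.** Both true. Cox is valid as a cause-specific analysis, so the remedy is a presentation rule and a label.

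**Conclusion.** The two follow-up rules in Section 5 contradict each other, and under the earliest-event rule the mortality outcomes in Section 8.2 cannot be measured as stated. This follows from the text alone. The size is uncertain: roughly 1 to 8 of 16 deaths missed, assuming 20% mortality in 80 patients, mean discharge at 10–30 days and a post-discharge hazard 0.1–0.5 times the in-hospital one. The plan should be corrected on this.

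The exposure TDM and the handling of death before recovery are real but smaller omissions in secondary analyses. If deaths were censored, 1 − KM would overstate 30-day recovery by about 5 to 6 points at 20% net mortality and the assumed constant hazards.

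A reader might also infer that the main result is compromised. It is not: measuring attainment at first and subsequent TDM is adequate for the primary proportion, and the 320 assays and 80 patients are unchanged.

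**What to change.** **Section 5.** Reconcile the two statements to one follow-up rule that ascertains vital status to day 30 in every patient regardless of discharge. Name the source for deaths after discharge, state one day-30 origin, and say whether end-of-therapy mortality is followed past discharge. Confirm that dates of death and of each TDM are recorded.

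**Section 8.2, exposure.** Name the TDM that classifies a patient as an attainer in the outcome correlations, and rule out ever having attained as a fixed exposure. First-TDM attainment is a simple main choice. Later attainment can be exploratory, as a landmark or time-varying analysis with the covariates already planned. If time zero is the first TDM, say how it relates to the day-30 mortality origin, since neither Section 5 rule counts from there.

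**Section 8.2, recovery.** Present days to defervescence and marker resolution by cumulative incidence with death as a competing event. Label Cox results as cause-specific, and state how discharge before recovery is handled.

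**Cost.** An amendment notified to the review board (Section 11), a day-30 vital-status check for about 80 patients, a few sentences in 8.2 and standard software. The downside is that first-TDM exposure ignores later dose changes, and the exploratory analyses will be imprecise at this size.
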